### 2.5.4 EEG Preprocessing and Analysis

EEGLab will be used to assess for quality and the presence of motion and eye movement artifact(Delorme and Makeig 2004). Data will undergo pre-processing with band-pass filtering from 0.1-50 Hz with 1st order Butterworth filters. Frontal channels will be assessed for eye movement artifact. Reduction of severe eye movement artifacts will employ independent component analysis approaches in EEGLab. The following analysis time epochs will be evaluated for secondary outcomes related to EEG activity: pre-ECT and post-ECT periods with either eyes open or eyes closed, the interval between anesthetic induction to and ECT stimulation, the period between stimulus delivery and cessation of ictal waveforms/spike-and-wave complexes, postictal period of EEG suppression and slowing, and both 5-minute epochs flanking the return of responsiveness to verbal command.

Spectral analysis will be performed using the Chronux Toolbox(Mitra and Bokil 2008), including five tapers, time frequency bandwidth of 3, and 6-second non-overlapping time windows. Total power and peak amplitude will be computed within the delta (0.5-4 Hz), theta (4-8 Hz), alpha (8-13 Hz), and beta (13-30 Hz) bands. Coherence and phase lag will be computed using the Chronux toolbox. Global coherence(Cimenser, Purdon et al. 2011) and permutation entropy will be computed(Bandt and Pompe 2002). Quantitative measures will be derived from spectral and time-based analyses of the ictal EEG. These measures will evaluate seizure energy, periodicity, and symmetry, as well as propagation, and termination.

In parallel to power spectral analysis, we will track the time-varying connectivity between the measured brain regions. Data will be windowed into 5-10 second epochs within which several cross-channel connectivity metrics will be computed. These measures will include the Pearson correlation, directed entropy, and Shannon mutual information. Thus, windows will manifest different 'networks', each describing the association between channels (regions) according to its respective metric. These networks will be clustered into a set of distinct motifs, or microstates, by using a k-means algorithm with least-squares error criterion. Other methods to characterize the time-varying dynamics of the observed brain activity, including those based on network control theory, will also be considered.

Visualization and analyses of epileptiform EEG activity will be performed using Net Station and Persyst software (Persyst, Solana Beach, CA, USA), following interpolation of bad channels and re-referencing to the average signal. EEG dipole source localization, inter-hemispheric generalization, and phase-reversals will be assessed by epilepsy board-certified neurologists. Seizures will be staged according to the previously described three components of electrical seizures induced by ECT (phase I with initial 14-22 Hz rhythmic beta activity, phase II with arrhythmic polyspike activity, and phase III with rhythmic 2.5-3.5 Hz. spike/polyspike activity(Gerst, Enderie et al. 1982). Additionally, expanding on previous analyses of stationarity in epileptiform activity induced by ECT(Zoldi, Krystal et al. 2000), we will use high-density EEG to topographically map rhythmic sharp-wave discharges. To maintain rigor, evaluators will be blinded to the study intervention.

Structural MRI scans, including T1-weighted images will be used for source localization using Brainstorm software.

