#### **2.4.7.1 Outcomes** (Further details on instruments are provided in appendices)

#### Primary and Secondary Outcomes

Primary outcomes include: the temporal recovery profiles for cognitive task performance, as measured using the Cognition assessment battery (Basner, Savitt et al. 2015); times for the return of responsiveness to auditory command; and the presence of delirium, evaluated through the 3-Minute Diagnostic Assessment for CAM-defined delirium (3D-CAM)(Marcantonio, Ngo et al. 2014).

Secondary outcome measures based on the EEG will include definitions of the seizures by standard techniques using both expert reader interpretation and quantitative techniques (Haider, Esteller et al. 2016). Central seizure duration will be visually determined by clinician evaluation of the frontal-mastoid bipolar EEG ictal complexes. Additional measures will be calculated from windowed analyses of the high-density EEG: power spectral measures of the interval between anesthetic induction to delivery of ECT stimulus charge; the seizure envelope for 1-12 Hz EEG power; peak-to-peak amplitude, calculated from the difference in maximum and minimum voltages within 300 millisecond time; periodicity of epileptiform discharges; inter-hemispheric symmetry of seizure discharges; intra- and inter-hemispheric coherence. When possible, these measures and power spectral estimates will be derived different phase of the ictal waveforms(Gerst, Enderie et al. 1982). The following postictal EEG measures will be assessed: duration of postictal EEG suppression; power spectral parameters flanking the return of responsiveness to verbal command; power spectral parameters from eyes open and closed epochs, including assessments of the posterior dominant rhythm. Spatiotemporal analyses will also focus on the propagation of EEG signatures during the ictal and early postictal period.

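### Channel-level correlation, mutual information and coherence are to be read as links between brain regions without leakage control, so an uneven change in slow-wave power can pass for a change in connectivity

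*Combined protocol and SAP*

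**What the plan says.** The Study Synopsis (section 1) lists functional connectivity and phase lag among the EEG outcomes. Section 2.5.4 states the target: "we will track the time-varying connectivity between the measured brain regions". The data are scalp recordings from 64 channels. "Data will undergo pre-processing with band-pass filtering from 0.1-50 Hz", and no further band split is stated for the network measures. "Data will be windowed into 5-10 second epochs within which several cross-channel connectivity metrics will be computed". On the choice of metric: "These measures will include the Pearson correlation, directed entropy, and Shannon mutual information". The resulting networks are described as "each describing the association between channels (regions) according to its respective metric", which treats a channel as a region, and they are then clustered by k-means into motifs. The same section adds "Coherence and phase lag will be computed using the Chronux toolbox", together with global coherence.

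For these measures the plan names no surface Laplacian, leakage correction, surrogate network, adjustment for band power or defined zero-lag-insensitive index.

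Section 2.5.3 (Recovery in the Spontaneous EEG) hypothesizes that frontal predominance of delta or theta power predicts cognitive performance or delirium. It also compares the spectral measures across treatment sessions. Section 2.1.2 describes delta activity appearing after the seizure and giving way to faster rhythms.

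**The concern.** Each scalp channel records a mixture of the same underlying sources. Correlation, mutual information and ordinary coherence between two channels are therefore above zero even when no sources interact, and they depend on how strong the shared sources are relative to the rest. If slow-wave power rises more in one area than elsewhere, these measures can change although nothing about the interaction between regions has changed. Motifs clustered from them can change too.

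A frontal rise in slow power is one of the plan's own hypotheses. A connectivity difference reported from these measures could then not be told apart from the band-power difference reported beside it. What is at stake is the reading of an exploratory EEG outcome, not a primary outcome or the sample size.

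**Working it through.** The plan gives no figure for this point, so there is none to reproduce. The check is of the mechanism, first by hand and then by simulation.

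**Step 1: two channels, no interaction.** Let channel 1 = s + n1 and channel 2 = 0.5s + n2, with s, n1 and n2 independent and of unit variance.

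- Start: covariance 0.5, variances 2 and 1.25, so r = 0.5/√(2 × 1.25) = 0.32.
- Amplitude of s doubled (variance 4): covariance 2, variances 5 and 2, so r = 2/√(5 × 2) = 0.63.
- Gaussian mutual information, −½ log2(1 − r²), rises from −½ log2(0.9) = 0.08 to −½ log2(0.6) = 0.37 bits.
- Coherence at a given frequency follows the same formula. The imaginary part of coherency is zero in both cases.

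**Step 2: simulation with true connectivity zero.** From the plan: 64 channels, a first-order Butterworth filter at 0.1-50 Hz, and the spectral settings "five tapers, time frequency bandwidth of 3, and 6-second non-overlapping time windows". Assumed, because the documents give no values: 150 independent 1/f sources, a radial-dipole forward model, effective source radius 0.60 or 0.75 of the head radius, sensor noise 15% of signal SD, a frontal patch of 15 sources, delta power raised 4- or 10-fold, and 40 windows per condition. Results with average reference:

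| Measure | Radius | Baseline | Repeat, no change | Frontal delta ×4 | Frontal delta ×10 | Delta ×10, all sources |
|---|---|---|---|---|---|---|
| Mutual information, frontal pairs (bits) | 0.60 | 0.208 | 0.203 | 0.232 | 0.262 | 0.296 |
| | 0.75 | 0.112 | 0.111 | 0.127 | 0.153 | 0.199 |
| Delta coherence, frontal with other channels | 0.60 | 0.207 | 0.197 | 0.238 | 0.286 | 0.212 |
| | 0.75 | 0.098 | 0.101 | 0.116 | 0.144 | 0.105 |
| Global coherence | 0.60 | 0.179 | 0.185 | 0.242 | 0.339 | 0.181 |
| | 0.75 | 0.087 | 0.088 | 0.124 | 0.206 | 0.088 |
| Mean absolute r, frontal with other channels | 0.60 | 0.212 | 0.208 | 0.226 | 0.249 | 0.226 |
| | 0.75 | 0.121 | 0.122 | 0.126 | 0.139 | 0.148 |

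The direction was the same without average reference. Not every pair moved: at radius 0.75 with frontal delta ×4, correlation and delta coherence within frontal pairs stayed at 0.205 and 0.189. Rescaling the whole signal fourfold changed none of the measures beyond repeat-to-repeat noise.

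**Step 3: motifs.** Two-cluster k-means separated the conditions clearly in one setting only: 82% correct (chance 50%) at radius 0.60 with average reference and frontal delta ×10. In the other three settings with the same power change it reached 51-59%.

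**Step 4: a zero-lag-insensitive index.** The weighted phase-lag index (delta, frontal pairs, average reference) went from 0.031 to 0.036 (×4) and 0.039 (×10) at radius 0.60, and from 0.046 to 0.047 and 0.039 at radius 0.75. Conditions with no power change, or with plain rescaling, ranged over 0.031-0.050, so this is its noise floor.

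That shows its behavior only where no interaction exists. Where interaction does exist, take two unit-power signals with imaginary coherency 0.5 and add one independent source equally to both channels. With added power 1, the imaginary part is 0.5/(1 + 1) = 0.25; with added power 4, it is 0.5/(1 + 4) = 0.10. The interaction is the same in both.

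**The case against.** Several points on the other side stand, and they limit what can be said.

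- A reader might infer that the plan tests connectivity between treatments and that those tests would falsely reject at some high rate. No such test is written down. The explicit comparison across sessions in section 2.5.3 is of spectral measures, and the networks in section 2.5.4 are used descriptively. A connectivity comparison is only implied by its listing as an outcome in a crossover, so no rejection rate can be assigned.
- A reader might extend the point to the secondary outcome "intra- and inter-hemispheric coherence" in section 2.4.7.1. That item closes a list of seizure measures, and the separate postictal list there contains no connectivity measure. Ketamine + sham ECT has no seizure, so this outcome cannot support a contrast between ketamine + ECT and ketamine + sham ECT.
- A reader might infer that source localization depends wholly on the optional MRI (section 2.4.7.3). Section 2.5.4 also plans dipole localization by neurologists with no MRI condition. It concerns epileptiform activity, however, and neither form of localization is linked to the connectivity measures.
- Phase lag is already planned, and connectivity is run in parallel with the spectral analysis, so part of the remedy exists. But phase lag is not defined as insensitive to zero-lag mixing, and it is not among the measures named for the networks.
- The suggested index is not immune to power either, as step 4 shows.
- Section 2.5 calls the study exploratory. That lowers the weight of the point, but it does not separate a connectivity finding from a power finding.

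**Conclusion.** The point holds in a conditional form. Section 2.5.4 reads channel-level association as connectivity between regions without leakage control, and a spatially uneven change in slow-wave power can shift the measures with no change in interaction.

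Relative to baseline, at radius 0.60 and 0.75 respectively, a fourfold frontal delta rise increased:

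- mutual information by 12% and 13% (0.232/0.208; 0.127/0.112);
- delta coherence by 15% and 18% (0.238/0.207; 0.116/0.098);
- global coherence by 35% and 43% (0.242/0.179; 0.124/0.087);
- mean absolute correlation by 7% and 4% (0.226/0.212; 0.126/0.121).

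The last is barely beyond the repeat run at radius 0.75. These sizes depend on the assumed source spread and on power gains that the documents do not give. A scalp-wide delta rise moves mutual information and, less, broadband correlation, but leaves within-band coherence essentially unchanged. The effect on the motifs is possible rather than general. Directed entropy was not checked. This is a low-cost improvement to an exploratory outcome and touches no primary analysis.

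**What to change.** In section 2.5.4:

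1. Define the planned phase-lag measure as a zero-lag-insensitive index, either the weighted phase-lag index or the imaginary part of coherency, from the cross-spectra already needed for coherence.
2. Require support from that index before stating that connectivity between regions differs.
3. Report Pearson correlation, mutual information, coherence and global coherence as sensor-level association, read beside band power for the same windows.

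The cost is a change of wording and one derived measure, with no new data, visits or patients. Settling it before analysis also removes the freedom to choose among metrics afterwards. There are two downsides to disclose: true zero-lag interactions will be missed, and the imaginary part of coherency can still be attenuated when independent power rises, so it too must be read with band power.

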### 2.7. Management of Intercurrent Events

### 2.7.1 Cross-over, repeated measures

18

The study design has a built in cross-over, repeated measures to allow patients to serve as their own control and to experience each of the treatments twice.

### 2.7.2 Adverse Experiences and Premature Discontinuation

The Washington University HRPO and the Data and Safety Monitoring Committee (DSMC) oversee the study's progression and adherence to protocol. Following each intervention, the principal investigators will affirm continued involvement or withdrawal based on patient tolerance and data quality. All adverse events will be reviewed by the DSMC and reported to HRPO, following the reporting policies and procedures, and followed until satisfactory resolution. The description of the adverse experience will include the time of onset, duration, intensity, known etiology, relationship to the study, and any treatment required. The trial steering committee will be responsible for all major decisions regarding changes to the protocol. The committee will communicate these changes to HRPO and appropriate parties. .

### 2.7.3 Potential Risks

**Interruption of clinical care:** While this is a theoretical risk, it is not envisaged that the conduct of this study will interfere with clinical care.

**Discomfort related to EEG/EMG/EOG:** Skin abrasions from scalp electrode placement or discomfort on removal of electrodes.

**Non-contrast MRI:** Claustrophobia, anxiety, discomfort from headphones used to shield out noise, or hearing loss due to hammering noise are all potential risks of undergoing non-contrast MRI. Patients with tattoos may experience irritation, swelling, heating, or instances of primary or secondary burns in the area of the tattoo. Additionally, patients with devices such as a pacemaker, bone hardware, or a device placed in their uterus may experience heating or movement of the device, device malfunction, or damage to the tissue that surrounds the device. These risks are unlikely to be common or severe.

**Breach of Confidentiality:** Another potential risk of participating in this study is that confidential information about the participant may be accidentally disclosed. We will use our best efforts to keep the information about participants secure, through de-identification of personal health information. We think the risk of accidental disclosure is very small.

#### 2.8 Procedures to Minimize Potential Risks

**Interruption of clinical care:** The research team will be in open discussion with patients and nursing staff to ensure that there is no disruption in the patient's clinical care, comfort, and recovery.

**EEG/EMG/EOG:** Timing and manner of electrodes and adhesive removal will be based on patient's comfort and convenience. Discomfort will be minimized based on the use of sticker/adhesive/gel electrodes and not needle electrodes.

**Confidentiality:** This will be maintained by assigning each participant a number to be linked with data. Any protected health information of patient participants will be stored in a locked drawer within the locked office of the PI. Electronic protected health information will be stored on a password-protected server.

**MRI Safety:** The patient will be thoroughly screened for MRI-incompatible implants. Scans may be performed following completion of the patient's ECT treatment course at Barnes-Jewish Hospital. Scans will be performed within the hospital (10th floor CCIR).

**Research Conduct:** Studies are conducted at Washington University School of Medicine under the general supervision of a board-certified cardiac anesthesiologist who is familiar with postoperative surgical care. Patients will be monitored during emergence and recovery from anesthesia by the anesthetic and nursing staff in the ECT suite as per standard care. Additionally, research personnel trained in good clinical practices will be present during the acquisition of data. Monitoring and safety will be according to the current clinical standard. Patient confidentiality will be maintained through de-identification of personal health information. Identity and

linking information will be stored in a locked cabinet within the principal investigator's office, which is locked outside of business hours. Electronic data will be password-encrypted on secure servers.

Patient satisfaction will be monitored throughout the study. Ketamine may improve the efficacy of ECT and recovery of cognitive function following ECT. Patients may benefit from the additional EEG monitoring in the postictal period during which non-convulsive status epilepticus is rarely manifested. Patients will be withdrawn if discontinuation is in the best interest of the patient or if the patient requests withdrawal or removal of treatment blinding. In the event that a patient's condition significantly worsens and requires additional or different interventions from those allocated in the study, the patient will be released from the study and data collection will be discontinued. Participants are given a satisfaction survey to be returned by mail following the last study session(Sienaert, De Becker et al. 2005).

**Participant Satisfaction:** During the follow-up phone call for the last study session, participants will be asked about their satisfaction in the study(Sienaert, De Becker et al. 2005).

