### 2.4.7.2 Data Collection

Outcomes, such as delirium assessments, will be entered into the Washington University School of Medicine Research Electronic Data Capture (REDCap) application. The baseline medications will be collected from the electronic medical record. The anesthetic and recovery record will be retrieved from the hospital's perioperative electronic medical record (Metavision by *i*MD*soft*®, Needham, MA). The cognitive assessments will be

completed using the COGNITION cognitive battery designed at the University of Pennsylvania(Basner, Savitt et al. 2015). The computer-based depression questionnaire will be completed through assessmentcenter.net developed by Northwestern University's Department of Medical Social Sciences. As standard care for tracking depression symptoms during an ECT course, treating psychiatry teams will administer the Quick Inventory of Depressive Symptomatology, Self-Report (16-Item), QIDS-SR16(Rush, Trivedi et al. 2003). To fully assess each patient's treatment response to ECT, the research team will use the electronic, as well as paper, medical records to access and record the following information for each treatment from the patients' entire ECT treatment course at Barnes-Jewish Hospital: QIDS scores, reason for treatment (diagnosis), the method of ECT (right-unilateral, bilateral, or bifrontal), treatment number, date of treatment, any medications including doses, charge/treatment parameters, central and peripheral seizure duration, any adverse events from the sessions, and any clinical notes regarding treatment efficacy or recovery from each procedure.

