### 2.8.1 Adverse Event Reporting and Data and Safety Monitoring Plan

The investigators will monitor subjects for evidence of adverse events. All adverse events will be reported to the IRB following the IRB reporting policies and procedures and followed until satisfactory resolution.

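### Ending data collection when a worsening patient is released conflicts with following adverse events to resolution and with chart extraction over the whole ECT course

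*Combined protocol and SAP*

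**What the plan says.** Four places in the combined protocol and SAP bear on this.

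- **Section 2.8 (Procedures to Minimize Potential Risks).** The trigger has two parts, both required: "In the event that a patient's condition significantly worsens and requires additional or different interventions from those allocated in the study". The consequence is that "the patient will be released from the study and data collection will be discontinued".
- **Section 2.7.2 (Adverse Experiences and Premature Discontinuation).** All adverse events go to the DSMC for review and are "reported to HRPO, following the reporting policies and procedures, and followed until satisfactory resolution". The content of each record is also fixed: "The description of the adverse experience will include the time of onset, duration, intensity, known etiology, relationship to the study, and any treatment required".
- **Section 2.8.1 (Adverse Event Reporting and Data and Safety Monitoring Plan).** The duty is repeated: "All adverse events will be reported to the IRB following the IRB reporting policies and procedures and followed until satisfactory resolution".
- **Section 2.4.7.2 (Data Collection).** The research team extracts from the medical record, "for each treatment from the patients' entire ECT treatment course at Barnes-Jewish Hospital: QIDS scores", together with "any adverse events from the sessions, and any clinical notes regarding treatment efficacy or recovery from each procedure".

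None of the last three makes an exception for a released patient, and section 2.8 makes none for safety follow-up or chart data. Section 2.5.1 mentions missing data only where it introduces mixed-effects models for cognitive recovery. No missingness assumption, sensitivity analysis or rule for data after release is given for any outcome.

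**The concern.** For a released patient whose adverse event is still open, one section tells the site to stop collecting data and two others tell it to carry on. A site that follows section 2.8 literally stops when the later duration of the event, its outcome and the treatment given would become known.

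The statistical difficulty is that release depends on how the patient is doing. Depression, mood and suicidal ideation are listed outcomes in the synopsis, and section 2.5.3 states an expected ordering of the three treatments for mood and depression. If later observations are missing because the patient got worse, what remains may look better than the course of the patients enrolled. The DSMC, for its part, could see an event open without seeing it close.

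**Working it through.** The plan gives no figure on this point, so there is nothing to reproduce. The main check is a comparison of the texts, followed through for one patient.

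**Step 1: a released patient with an open adverse event.**

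| Item | Section 2.8, read literally | Other sections |
|---|---|---|
| Events and scores recorded before release | Kept; nothing says they are deleted | Kept |
| Resolution and full duration of the open event | Not collected | Required (2.7.2, 2.8.1) |
| Treatment the event required | Not collected if given after release | Required (2.7.2) |
| Later QIDS scores and adverse events in the chart | Not collected | Collected to the end of the ECT course (2.4.7.2) |
| Later PROMIS-CAT, mood manikin, suicidal ideation items | Not collected | Tied to study sessions (2.3.8, Table 1), so they end with release anyway |

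Rows two to four conflict. Row three is the sharpest: needing other interventions is part of the release trigger, and treatment required is a mandatory item of the adverse-event record.

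**Step 2: can the term be read narrowly?** Data collection in section 2.8 might mean study testing only, but the text does not say so. The protocol's own section with that title, 2.4.7.2, covers the chart extraction, so the natural reading includes it.

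**Step 3: are the later data informatively missing?** Release follows worsening. A likelihood-based mixed model that uses the data before release copes if release depends only on what was already recorded. It does not if the worsening appears after the last recorded measure. The plan commits to neither assumption, and it mentions missing data only for cognition.

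**Step 4: scale, for illustration only.** Documented inputs are 15-20 patients (section 2.6) and six experimental sessions each (section 2.3.1). Section 2.6 expects attrition but gives no rate. Assume 1 to 3 patients are released.

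- Share of patients: 1/20 = 5.0% to 3/15 = 20.0%.
- Sessions not held, w × (6 − k) out of 6N, for w patients released after session k: from 1 × (6 − 5) = 1 of 120 (0.8%) to 3 × (6 − 1) = 15 of 90 (16.7%). This loss comes from release itself, and changing the data-collection rule would not recover it.
- Shift in an endpoint mean over retained patients only, (w/N) × D, if released patients would have ended D = 0.5 to 2 SD worse: from (1/20) × 0.5 = 0.025 SD to (3/15) × 2 = 0.40 SD.

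The counts w, the session k and the difference D are assumptions. The last line also describes a summary that the plan does not specify. It shows how the arithmetic works and does not estimate bias in a planned analysis.

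**The case against.** The strongest reply is that section 2.8 is about leaving the experimental protocol, while sections 2.7.2 and 2.8.1 impose specific duties covering all adverse events. A sensible site would stop sessions and testing and still follow an open event. QIDS is collected by the treating team as standard care, so the scores would exist whatever the study does. The study is declared exploratory, its primary outcomes are measured within a session, and mood and depression are secondary. The consent pages are not in the public copy, so they may already cover data after release.

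Much of this stands. It shows that the conflict is easy to resolve and that the primary outcomes are not shown to be affected. It does not show that the text resolves the conflict: section 2.8 gives an instruction without exception, and a site that follows it does nothing wrong by that section. That QIDS scores exist in the chart does not help if the study stops extracting them.

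Several stronger readings are tempting, and the documents do not support them.

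- **Worsening alone stops data collection.** A need for other interventions is also required.
- **The worst courses disappear, or their events are never recorded.** Only data after release are at risk. Events are reviewed as they occur, a coordinator contacts each patient within 24 hours of a study day (section 2.3.8), and nothing says earlier records are dropped.
- **Release will be unbalanced across treatments.** Section 2.5.3 expects the least improvement with ketamine plus sham ECT, which is not a prediction of worsening, and each randomized block contains all three treatments.
- **A request for unblinding also ends data collection.** That sentence says the patient is withdrawn and does not mention data collection.

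**Conclusion.** The conflict is real and can be confirmed by reading the sections together. For a patient released under section 2.8, the plan both stops and requires follow-up of an open adverse event, and both stops and requires chart extraction for the rest of the ECT course. Taken literally, section 2.8 loses follow-up after release in patients selected for worsening. That loss is plausibly informative for the secondary mood and depression outcomes, and it weakens DSMC review.

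The size of any bias cannot be derived. A reader might be tempted to quote a shift in QIDS points, but the documents give neither a release rate nor a difference between released and retained patients, and no analysis of retained patients only is planned. No formal safety analysis is specified either, so the safety consequence is incomplete adverse-event records and not a distorted test. The conclusion rests on the wording alone and does not depend on the illustrative figures.

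**What to change.** Reconcile sections 2.8, 2.7.2, 2.8.1 and 2.4.7.2.

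- In section 2.8, state that release ends the experimental sessions and study testing only.
- State that, unless the patient withdraws consent for data use, adverse events continue to be followed to resolution and reported to the DSMC and HRPO, and the section 2.4.7.2 extraction (QIDS, adverse events, later treatments) continues to the end of the ECT course.
- In section 2.5, state how data after release are handled for mood and depression, including the missingness assumption and a simple sensitivity analysis.
- Report the number of patients released and the last treatment each received before release.

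When to release a patient is a clinical decision for the sponsor and is not touched by this change.

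The cost is about one sentence in section 2.8, a short addition to section 2.5, and a check that the consent wording covers data after release. The chart extraction and adverse-event follow-up are already planned for every patient, so no visits are added.
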